6 RESEARCH METHODS

6.1 Study Design

This will be a non-interventional multi-center cohort study of patients initiating inebilizumab conducted with secondary data sources in France, Germany, Italy, the Netherlands, and Spain. The study will be based on a cohort-event monitoring design to capture both drug utilization and selected safety outcomes in patients initiating inebilizumab. The proposed study design allows for an efficient initial descriptive evaluation of AESI.

The **study period** in individual countries will start on different dates, depending on the launching time of the drug (the earliest in the second quarter of 2022) (Table 1). The end of the study period will be also country-specific (the latest in December 2027) and will depend on the dates of data availability in individual data sources (different lag times and data release dates).

Table 1 Study periods, by country

	France	Germany	Italy	Netherlands	Spain
	SNDS/ NOMADMUS	GKV	RISM	PHARMO	SIDIAP
Launch date (quarter, year)	Q2, 2022	Q3, 2022	Q2 2023	Q3, 2023	Q2, 2023
Start of study period	May 2022	Aug 2022	May 2023	Aug 2023	May 2023
End of study period	Dec 2026	Dec 2026	Dec 2027	Dec 2026	Sep 2027
Study period duration (months)	57	54	56	41	53

Q2, 2nd quartile; Q3, 3rd quartile

The study population will be constituted by a cohort of adult female and male patients diagnosed with NMOSD with entry trigger by inebilizumab initiation.

[figure not shown]
The **index date** (Day 0) will be defined as the date of first treatment (date of administration/prescription/dispensation, depending on data available in selected data sources) (Figure 1). Patients initiating the treatment will be identified throughout the study period. After the index date, enrolled patients will be followed for 12 months or censored at end of study period or loss of follow-up (death, disenrollment/de-registering) whichever occurs first.

A **baseline period**, including any time from when data are available up to the index date, will be used to establish comorbidities and NMOSD-related clinical characteristics, whereas a short period of 6 months prior to or at index date will be used to determine previous immunosuppressive therapies.

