6.3.3 Treatment patterns

During follow-up, treatment patterns will be characterized in terms of dose, treatment duration, frequency of drug discontinuation, switching and use of add-on therapies. All patients included in the study will be deemed exposed (at least one inebilizumab treatment), but only those with complete 12-month follow-up will be considered in the evaluation of the treatment patterns as described below.

According to the product specifications, the 12-month follow-up will cover 3 potential inebilizumab administrations: initial intravenous (IV) infusion followed by a second

infusion 2 weeks later and a subsequent infusion 6 months after the first treatment (Figure 2A). The first and third infusion will be considered in defining inebilizumab treatment patterns.

Treatment duration will be the sum of days under inebilizumab exposure during the follow-up. Number of days under exposure will be calculated for the first and the third infusion as the difference between end date of inebilizumab exposure period and the administration/prescription/dispensation date (Figure 2B).

[figure not shown]
Inebilizumab complete **exposure period** will be assumed to last 180 days after drug administration/prescription/dispensation. The **end date of the exposure** period will be defined as the end of each inebilizumab exposure period within follow-up or the end date of follow-up if comes first (Figure 2B).

A patient will be considered to be in inebilizumab **continuous use** if no gap longer than 60 days occurs between the end date of the first inebilizumab exposure period and the beginning of the third (2B). **Temporary discontinuation** (intermittent users) will be defined in patients with gaps between inebilizumab exposure periods longer than 60 days but with a subsequent inebilizumab administration/prescription/dispensation during the follow-up. A patient will be defined as having **permanently discontinued** inebilizumab if no subsequent inebilizumab treatment is registered during the follow-up after the end date of the first inebilizumab exposure period.

Switchers will be a subgroup of patients who discontinue inebilizumab (temporarily or permanently) during the follow-up and have other NMOSD maintenance drug administered/ prescribed (Table 9) after the end date of inebilizumab exposure period (2C). The alternative NMOSD drugs will be described.

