6.7.2.3 Objective 3: Incidence of AESI

The AESI evaluated in this study include the following categories: serious infections, opportunistic infections, hepatitis B reactivations, infusion related reactions, and malignancies. Analysis of AESI will include estimation of the cumulative incidence (i.e., risk), incidence rate, and time to AESI onset ([Table 5](#)). All analysis for AESI events (i.e., cumulative incidence, incidence rate and time-to-onset) will be performed using an intention-to-treat approach i.e., patients will be considered exposed regardless of subsequent discontinuation.

The cumulative incidence (with 95% CI) will be calculated separately for each AESI category considering the overall study population. For all AESI categories, except infusion related reactions, the cumulative incidence (with 95% CI) will be calculated as the total number of incident reports of AESI during the follow-up divided by the total number of patients. An algorithm to identify incident reports of AESI will be developed and described in the SAP. For infusion related reactions, the cumulative incidence (with 95% CI) will be calculated as the total number of all reports of infusion related reactions on the day of infusion (if date of inebilizumab administration is available) or during the first 3 days following prescription/dispensation (if date of inebilizumab administration is not available), divided by the total number of patients in the overall study cohort. Additional details of this calculation will be provided in the SAP.

The cumulative incidence estimates for each AESI category, except infusion related reactions, may also be calculated for shorter periods e.g., in monthly intervals after index date. In this case, the cumulative incidence in the first month after index date would consider patients with AESI reports in the first month in the numerator and patients with complete 12-month follow-up in the denominator. The cumulative incidence in the second month would consider patients with reports recorded only in the second month in the numerator and patients with complete 12-month follow-up included in the denominator. Due to the limited sample size, the time intervals may need to be clustered into e.g., 3-month intervals with the numerator and denominator adjusted accordingly. If sample size permits, the difference (with 95% CI) in cumulative incidence between 2 time periods of observation may be calculated.

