The incidence rate and time to onset of AESI will be estimated in the overall study population. The incidence rates will be estimated separately for each AESI category, except infusion related reactions, as the total number of first reports of an AESI divided by the time at risk of the patients. The patients' time at risk will be counted from the initiation of inebilizumab treatment until occurrence of AESI, end of the 12-month follow-up or censoring. Incidence rate will be expressed as the number of first reports of an AESI per 1,000 patient-months.

Kaplan-Meier estimates of the median time from index date to AESI onset will be provided separately for each AESI category, except infusion related reactions, if number of events allows. If there is no AESI during the follow-up, the patient will be censored at the end of follow-up. Descriptive statistics on the time-to-event will be provided in further detail in the SAP.

Table 5 Overview of estimates of incidence and time to event defined for objective 3.

AESI category	Estimate	Time at risk	Event	Population
Infusion related reactions	Cumulative incidence	Day of infusion if date of inebilizumab administration available or 3 days following prescription/dispensation	All recorded reactions	Overall population
Serious Infections / Opportunistic infections	Cumulative incidence	12 months	All recorded infections during the follow-up	Overall population
	Cumulative incidence	Short periods	First infection during follow-up	Patients with complete 12-month follow-up
	Incidence rate	From index date to AESI, end of follow-up or censored*	First infection	Overall population
	Time to event	From index date to AESI end of follow-up or censor*	First infection	Overall population
Hepatitis B reactivations	Cumulative incidence	12 months	All recorded reactivations during the follow-up	Overall population
	Cumulative incidence	Short periods	First reactivation	Patients with complete 12-month follow-up
	Incidence rate	From index date to AESI end of follow-up or censor*	First reactivation	Overall population
	Time to event	From index date to AESI, end of follow-up or censor*	First reactivation	Overall population

AESI category	Estimate	Time at risk	Event	Population
Malignancies	Cumulative incidence	12 months	All recorded malignancies during the follow-up	Overall population
	Cumulative incidence	Short periods	First malignancy	Patients with complete 12-month follow-up

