	Incidence rate	From index date to AESI end of follow-up or censor*	First malignancy	Overall population
	Time to event	From index date to AESI, end of follow-up or censor*	First malignancy	Overall population

* Censoring criteria will be the earliest of permanent treatment discontinuation, loss to follow-up (death, disenrollment/de-registering) or end of study period.

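### AESI incidence rates and time to onset are declared intention-to-treat in Section 6.7.2.3, but the Table 5 footnote censors them at permanent discontinuation

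*Protocol*

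**What the plan says.** Section 6.7.2.3 opens with a general rule for AESI. It names cumulative incidence, incidence rate and time to onset, and says the analyses "will be performed using an intention-to-treat approach i.e., patients will be considered exposed regardless of subsequent discontinuation". Later in that section, time at risk for the rate runs "until occurrence of AESI, end of the 12-month follow-up or censoring", with censoring left undefined at that point. For Kaplan-Meier the text reads: "If there is no AESI during the follow-up, the patient will be censored at the end of follow-up".

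Table 5 then defines time at risk for the rate and time-to-event rows as "From index date to AESI, end of follow-up or censored", with an asterisk. The footnote to that asterisk reads: "Censoring criteria will be the earliest of permanent treatment discontinuation, loss to follow-up (death, disenrollment/de-registering) or end of study period".

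The design text in Section 6.1 has no such criterion: "enrolled patients will be followed for 12 months or censored at end of study period or loss of follow-up (death, disenrollment/de-registering) whichever occurs first". Footnote b of Figure 1 and the abstract also omit discontinuation.

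Section 6.3.3 classes a patient as having permanently discontinued if "no subsequent inebilizumab treatment is registered during the follow-up after the end date of the first inebilizumab exposure period". It sets the exposure period at 180 days and evaluates treatment patterns only in patients with complete 12-month follow-up.

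**The concern.** The footnote holds the only on-treatment rule in the protocol, and it contradicts the text that the table summarises. It is not labelled as a supplementary analysis. The SAP cannot settle this by adding detail: the protocol fixes both rules, so following one departs from the other.

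The footnote rule also has three faults of its own.

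- **It looks ahead.** Whether a patient has permanently discontinued is known only when the 12 months are over, so censoring at an earlier date conditions on later records.
- **It is undefined for part of the population.** Section 6.3.3 gives the status only for patients with complete 12-month follow-up, while Table 5 applies it to the overall population. A patient lost at month 8 has no stated classification.
- **The censoring may be informative.** Patients who stop may differ in AESI risk, and Section 6.9 says that reasons for discontinuation cannot be captured.

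Quantifying AESI is Objective 3 of this safety study. If the footnote is followed, the three measures reported side by side would cover different risk periods under one intention-to-treat label. Analyses are run by data source, possibly by third parties, so different programmers could also apply different rules.

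**Working it through.** **Which rows are affected.** The asterisk is on incidence rate and time to event for three groups: serious/opportunistic infections, hepatitis B reactivations and malignancies. That makes 3 × 2 = 6 rows. Cumulative incidence rows carry no asterisk. Infusion related reactions have cumulative incidence only, so they are untouched.

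**The rules side by side.**

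| Place | Does discontinuation end time at risk? |
|---|---|
| Abstract; 6.1; Figure 1 footnote b | Not listed |
| 6.7.2.3, opening paragraph | No, for all three measures |
| 6.7.2.3, Kaplan-Meier text | No; event-free patients run to end of follow-up |
| Table 5 footnote | Yes |

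**The protocol's own size figure.** Table 3 uses n = 1.96² × p(1 − p)/w². With p = 1% and w = 1% this gives 380.3 (stated 380); with p = 4% and w = 2% it gives 368.8 (stated 369). The size calculation is not in dispute. It supplies the 400 patients and the 4% incidence used below.

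**Assumptions.** The protocol gives no discontinuation fraction, no AESI rate and no discontinuation date. I assume:
- censoring of permanent discontinuers at day 180, the end of the first exposure period;
- full 12-month follow-up, and person-time not shortened by events;
- a fraction d discontinuing, and a hazard after stopping of h times the hazard before.

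**Person-time lost** = d × (365 − 180)/365 = d × 0.507.
- d = 10%: 5.1%
- d = 20%: 10.1%
- d = 30%: 15.2%

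For 400 patients the intention-to-treat rule gives 400 × 12 = 4,800 patient-months. With 180 days = 5.91 months, the footnote rule gives 400 × (12 − d × 6.09), that is 4,557, 4,313 and 4,070 patient-months.

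**Events dropped and rate ratio at d = 20%.** Let L = 0.2 × 185/365 = 0.101.
- Share of events dropped = hL/(1 − L + hL)
- Intention-to-treat rate ÷ footnote rate = 1 − L + hL

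| h | Events dropped | Rate ratio |
|---|---|---|
| 0.5 | 5.3% | 0.95 |
| 1 | 10.1% | 1.00 |
| 2 | 18.4% | 1.10 |
| 3 | 25.3% | 1.20 |

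**In the protocol's units.** A constant rate of 4% over 12 months is 0.04/12 × 1,000 = 3.33 per 1,000 patient-months. The footnote rule returns 3.33 whatever happens after stopping. At d = 20% the intention-to-treat rule returns 3.16, 3.33 or 3.67 for h = 0.5, 1 or 2. For h from 0 to 2 the rate ratio spans 0.95 to 1.05 at d = 10%, 0.90 to 1.10 at d = 20%, and 0.85 to 1.15 at d = 30%.

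**The case against.** The strongest reply is that the intent is plain and the effect small. The governing sentence names all three measures, the design section agrees with it, and one footnote is the outlier, probably a drafting slip. The study tests no hypothesis. At 400 patients the planned precision is ±1 point on 1% (±100% relative) or ±2 points on 4% (±50% relative), wider than a shift of −5% to +20%. For the incidences in Table 3 (0.3% to 5%) a 12-month Kaplan-Meier median would not be reached under either rule. All of this is fair as to size. It does not remove the contradiction, since no text ranks one rule above the other. The shift is also systematic, so more patients would not reduce it.

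Day 180 is inferred, and the loss of 185 days is a ceiling. It applies only to patients with full follow-up and no earlier event in that category. Both points stand.

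It is also said that a patient who stops because of a serious infection has already contributed that first event. This holds when the event precedes the censoring date. It fails when the event follows it. Section 6.3.3 allows a gap of up to 60 days within continuous use. A patient with an infection on day 200 and no later infusion is therefore classed as a permanent discontinuer. Under the day-180 reading, that infection is then discarded. Events in other AESI categories after stopping are lost in the same way.

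**Conclusion.** The protocol is wrong as written. It sets two incompatible censoring rules for the incidence rate and time to onset of every AESI category except infusion related reactions. Cumulative incidence is not affected.

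Under the stated assumptions, the footnote removes at most 5% to 15% of person-time for 10% to 30% discontinuing. At 20% discontinuing, it moves the comparison of rates to between 0.95 and 1.20 for post-stopping hazards of 0.5 to 3 times the earlier one. With equal hazards the expected rate is unchanged, but about 10% of events and the precision they carry are still lost. The size rests on assumed fractions and hazards and an inferred censoring date. The contradiction rests only on the text.

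**What to change.** Delete permanent treatment discontinuation from the Table 5 footnote, so that it matches Section 6.1, Figure 1 and the intention-to-treat sentence in Section 6.7.2.3. Define censoring once and refer to that definition in the time-at-risk paragraph and the table.

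If an on-treatment rate is also wanted, list it as a labelled supplementary analysis. Give it a censoring date that can be fixed from records available up to that date and that applies to every patient in the overall population, including those with less than 12 months of follow-up.

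The cost is one footnote edit in a protocol amendment and matching SAP wording. No extra data are needed.

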6.8 Quality Control

The study will use existing databases, which are being used widely for research. The study will be executed in line with all applicable regulations and guidelines – such as best-practice guidelines applicable to non-interventional PASS, including but not limited to the ENCePP Guide on Methodological Standards in Pharmacoepidemiology (36), the ENCePP Checklist for Study Protocols, and the Guidelines for GPPs (38) of the International Society for Pharmacoepidemiology (ISPE) as well as the specific IQVIA Standard Operating Procedures on retrospective analysis. The study will be recorded in the European Union electronic register of post-authorization studies (EU PAS register) maintained by the European Medicines Agency.

For the IQVIA EU data sources, quality control is conducted at several levels depending on the database. At the database level, the quality unit of the production department of IQVIA verifies continuously the quality of its sources in terms of representativeness and consistency of collected data. All study programs, log files, and output files will be stored on the secure server. If the study is being conducted by a third party, the datasets and analytic programs will be stored according to the vendor’s procedures.

6.9 Limitations of Research Methods

Automated healthcare databases are appropriate for real-world studies due to the recording of prescriptions and clinical data from routine clinical practice, independently of any study purposes.

The use of secondary data allows the identification of all drug users which limits selection bias, since all patients fulfilling the inclusion criteria are included in the study. Inebilizumab is available in secondary care settings (hospitals and specialized centers) which narrows down the area of searching for eligible patients. This is particularly relevant to answer the research objectives due to the fact NMOSD is a rare condition and inebilizumab is expected to be used by a small number of individuals. Furthermore, the

inclusion of several countries contributes to the representativeness of European inebilizumab users.

However, some limitations should be addressed:

- Inebilizumab is a novel drug, so one can expect changes over time in clinical practice regarding the use of the drug. The uptake of inebilizumab in the population covered by the data sources may be slow at the beginning of the study period and is likely to increase closer to the end. This pattern may result in a small sample of patients with complete follow-up, i.e., eligible to answer objectives 2 and 3. Thus, treatment patterns and safety outcomes may lack precision. Additionally, long-term treatment patterns and safety outcomes will not be assessed in this study.
- Despite the anticipated high reliability and validity of the data sources proposed for the study, there may be a potential of under- or misreporting of diagnostic information. In addition to variation in ICD-10 coding practices across countries, NMOSD is a rare and complex condition, with wide extent of the diagnostic work-up and diverse diseases can mimic NMOSD (39), making a late diagnosis or potential misclassification more probable. NMOSD-associated conditions may also be prone to misclassification, particularly the less severe ones, which may underestimate their frequency.
- Data collected for administrative purposes may be incomplete for medical information not directly related to reimbursement. This can affect the measurement of variables to characterize inebilizumab users and safety outcomes, underestimating its frequency. When available, the use of disease registries may minimize this limitation.
- Data sources relying on drug prescription/dispensation - and not administration - may result in exposure misclassification and bias in the treatment patterns characterization and time-to-event analyses. Additionally, reasons for treatment discontinuation, switching or augmentation are not possible to capture not allowing the documentation of changes in treatment.
- Some variables, such as drug dose, laboratory results of biomarkers and exams such as MRI may not be available in all data sources which will limit comparability and the ability of a more detailed characterization of inebilizumab users in those countries.
- Other variables, such as treatment indication, if not available in the data sources, will be based on pre-defined algorithms.
- The evaluation of drug safety using secondary databases does not allow for a causal assessment between inebilizumab exposure and the experienced outcome. NMOSD has been shown to be highly associated with other diseases including cancer (40). Additionally, an increased risk of malignancies or serious infections in NMOSD may be induced by the exposure to other immunosuppressive therapies (41,42). Please note, most malignancies have long latency periods in the absence of immunosuppression (43), and although immunosuppressive therapies possibly shorten the period (44), current study follow-up time may be too short (up to 1 year is the maximum) to identify some malignancies. Therefore, safety outcomes should be considered as signals of a possible safety concern of inebilizumab exposure.
- This study will capture safety outcomes that were serious enough to come to medical attention, which may underestimate the frequency of mild events. Additionally, misclassification is a possibility as it relies on the diagnosis codes. Identified serious infections, serious infusion related reactions or malignancies

represent a subgroup of all serious adverse events but for which the validity is expected to be higher.

- For some data sources, reporting of small numbers (e.g., <5) requires compliance with the local policies regarding data anonymization and the risk of patients' identification in observational research. For example, if a real value is 2, it may need to be presented as ≤ 4 in the results table. This may be a potential limitation for analyses that require stratification, such as the number of malignancies in a specific age groups. Furthermore, minimum and maximum values cannot be reported.

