4 RATIONALE AND BACKGROUND

4.1 Background

Neuromyelitis optica spectrum disorder (NMOSD; also known as Devic's syndrome and previously known as neuromyelitis optica [NMO]) is a rare, chronic, autoimmune, inflammatory disorder of the central nervous system, characterized by attacks of optic neuritis and longitudinally extensive transverse myelitis and, less frequently, affecting the brain and brainstem (1). Commonly reported symptoms include ocular pain, unilateral or bilateral loss of visual acuity that can lead to blindness, loss of sensation, weakness (including paraplegia), bladder and bowel dysfunction, paroxysmal tonic spasms of the trunk and limbs, and Lhermitte's phenomenon (1). Up to 90% of patients with NMOSD have recurring episodes of optic neuritis and/or myelitis rather than following a monophasic course (2). Attacks can be severe and result in blindness, paralysis, and even death due to neurogenic respiratory failure (3). An important paraclinical feature of NMOSD seen in 80% patients and used to help differentiate the condition from multiple sclerosis (MS) is the presence of serum autoantibodies against aquaporin-4 (AQP4) (i.e., AQP4-immunoglobulin [Ig]G or NMO-IgG) (4).

Worldwide, incidence rates of adult NMOSD are reportedly between 0.04-0.73/100,000 person-years (5), while the prevalence of NMOSD in adults is approximately 0.5-4/100,000 and may be up to 10/100,000 in certain racial groups (6). NMOSD can occur at any age, and disproportionately affects females (70%-90%), with a mean age of onset of approximately 40 years (6).

Treatment of NMOSD comprises 2 main goals: recovery from acute attacks and prevention of future attacks (relapse) as well as prevention of sequelae.

Recently, inebilizumab, an anti-CD19 B-cell depleting antibody, was approved for the treatment of NMOSD in AQP4-IgG seropositive patients in the US, Japan, and South Korea, and in November 2021 the Committee for Medicinal Products for Human Use of the European Medicines Agency (EMA) also recommended approval for the same patient population. The current recommended initial dose is 300 mg intravenous (IV) infusion followed 2 weeks later by a second 300 mg IV infusion. The recommended maintenance dose is a single 300 mg IV infusion every 6 months thereafter, starting 6 months from the first infusion (7).

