At index date, patients will be described in terms of demographics, comorbidities, NMOSD-related clinical characteristics (disease duration, NMOSD core symptoms, differential diagnoses, NMOSD-associated conditions, history of relapses), previous immunosuppressive therapies, and inebilizumab initiation characteristics (setting of healthcare and specialty of prescribers and treatment indication).

As of the index date, data on inebilizumab treatment will be used to assess the 12-month treatment patterns, considering duration of treatment, dosing, frequency of the drug discontinuation, switching, and use of add-on therapies. AESI will be captured during the first 12 months following the index date. Cumulative incidence and incidence rates of AESI will be quantified for the overall follow-up period. Additionally, the estimates will be calculated for shorter periods of exposure (e.g., monthly) allowing the assessment of periods of higher or lower frequency of each outcome.

Figure 1 Study Design

Abbreviations: NMOSD, neuromyelitis optica spectrum disorder

^aFirst inebilizumab administration/prescription/dispensation, depending on the available data.

^bCensoring criteria will be the earliest of loss to follow-up (death, disenrollment/de-registering) or end of study period.

Data will be analyzed for the overall cohort of patients initiating inebilizumab and for sub-groups of special interest: patients concomitantly receiving other immunosuppressive agents and patients over 65 years of age at index date.

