9.3 Final Analyses and Reporting

A final study report will be generated after all data collection is complete, including up to 57 months of study period (Table 1). The final study report will be submitted as a standalone procedure to the competent authorities 12 months after the availability of final analytical data set. The final report will encompass all planned analyses, including a description of the complete study population, as described above and in the SAP.

In accordance with the 2010 EU pharmacovigilance legislation (Articles 10 or 10a of Regulation (EC) No 726/2004; Articles 21a or 22a of Directive 2001/83/EC) (46,47), information about this PASS will be entered into the publicly available EU PAS register (<http://www.encepp.eu/encepp/studiesDatabase.jsp>). The study protocol will be entered into the register before the start of data collection. Updates to the study protocol in case of substantial amendments, progress reports where applicable, and the final study report will also be entered in the register.

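### Malignancy follow-up stops at 12 months by choice, so objective 3 is answered for malignancies for year one only; a supplementary rate over all available follow-up would be a cheap gain

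*Protocol*

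**What the plan says.** Section 6.1 of the protocol sets one follow-up rule for all patients: "enrolled patients will be followed for 12 months or censored at end of study period or loss of follow-up". It then limits the safety outcomes in the same way: "AESI will be captured during the first 12 months following the index date". Section 6.7.2.3 counts time at risk for the incidence rate from treatment initiation "until occurrence of AESI, end of the 12-month follow-up or censoring". Table 5 applies this to malignancies, with a 12-month cumulative incidence, and with a rate and a time-to-event analysis that stop at end of follow-up.

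Entry is not confined to an early window: "Patients initiating the treatment will be identified throughout the study period". Table 1 gives country study periods of 41 months (Netherlands) to 57 months (France), and section 9.3 describes the final report as "including up to 57 months of study period". Section 6.2 plans annual data extraction.

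Section 5 limits research question 3 to the first 12 months. Specific objective 3, listed just below it, has no time limit, whereas specific objective 2 has one. Section 6.9 says that malignancies mostly have long latency without immunosuppression and that "current study follow-up time may be too short (up to 1 year is the maximum) to identify some malignancies". It also says that long-term safety is outside the study. No reason is given for choosing 12 months.

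**The concern.** Malignancy is the one AESI category for which the protocol itself says that its window may be too short. A patient who starts in 2022 and has a malignancy coded in month 15 contributes 12 event-free months. A low or zero malignancy count would then say little about anything beyond year one.

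The data sources do not impose the limit. Section 6.4 describes them as longitudinal: ten years of follow-up in the French national system, a mean of ten years in the Catalan database, and an average of twelve years in the Dutch network. Patients who enter early in a 41 to 57 month study period could be observed well past month 12 in the same sources. At stake is person-time for a rare outcome, in a study that already expects its safety estimates to lack precision (section 6.9).

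**Working it through.** **Study periods, from the dates in Table 1 (both end months counted).**

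- France, May 2022 to Dec 2026: 8 + 48 = 56 (stated 57).
- Germany, Aug 2022 to Dec 2026: 5 + 48 = 53 (stated 54).
- Italy, May 2023 to Dec 2027: 8 + 48 = 56 (stated 56).
- Netherlands, Aug 2023 to Dec 2026: 5 + 36 = 41 (stated 41).
- Spain, May 2023 to Sep 2027: 8 + 36 + 9 = 53 (stated 53).

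The French and German entries are one month high, which has almost no effect below. The first French patients could have about 44 months after month 12.

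**Assumptions.** The protocol gives no uptake curve and no attrition rate. I take entry density over a period of T months as uniform, linearly rising or quadratically rising. Section 6.9 expects uptake to increase towards the end, so the rising shapes are closer to the protocol. Attrition is 0% or 20% per year.

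**Formulas without attrition.** Let k = 1, 2, 3 for uniform, linear and quadratic entry.

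- Mean available follow-up: T/(k+1)
- Mean follow-up used under the 12-month limit: [T^(k+1) − (T−12)^(k+1)] / [(k+1)·T^k]
- Share left out: ((T−12)/T)^(k+1)
- Share of patients with more than 12 months to study end: ((T−12)/T)^k

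For T = 57 and uniform entry, available follow-up is 57/2 = 28.5 months. Used follow-up is (57² − 45²)/(2·57) = 1224/114 = 10.7 months. The share left out is (45/57)² = 62%.

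| T | Entry | Available (months) | Used (months) | Left out | Left out, 20%/yr attrition | Patients with >12 months |
|---|---|---|---|---|---|---|
| 57 | uniform | 28.5 | 10.7 | 62% | 53% | 79% |
| 57 | linear | 19.0 | 9.7 | 49% | 41% | 62% |
| 57 | quadratic | 14.3 | 8.7 | 39% | 32% | 49% |
| 41 | uniform | 20.5 | 10.2 | 50% | 43% | 71% |
| 41 | linear | 13.7 | 8.8 | 35% | 30% | 50% |
| 41 | quadratic | 10.3 | 7.7 | 25% | 21% | 35% |

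The last column ignores attrition. For the attrition column, potential follow-up f is replaced by (1 − e^(−hf))/h with h = −ln(0.8)/12 per month, integrated numerically over entry times. With T = 56 and no attrition the shares are 62%, 48% and 38%.

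**What this means for precision.** Take the 400 patients that section 6.5 uses as an illustration, all in a source of length T, with no attrition. Person-years are 400 × mean months / 12. With zero events, the upper 95% bound is about 3 / person-years.

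- T = 57, uniform: 358 rises to 950 person-years; the bound falls from 8.4 to 3.2 per 1,000 person-years.
- T = 57, quadratic: 290 rises to 475; the bound falls from 10.3 to 6.3.
- T = 41, quadratic: 256 rises to 342; the bound falls from 11.7 to 8.8.

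These bounds assume a constant rate. With latency the rate may differ by year, which is why the extended rate should also be shown by year since index.

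**The case against.** The strongest reply is that first-year incidence is what the study set out to estimate. Research question 3 and the abstract both say so. Section 6.9 discloses the consequence for malignancies, rules out long-term safety, and tells readers to treat safety results as signals only. That stands: the limit is declared scope, and a month-15 event is correctly outside a 12-month risk.

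A reader might infer several stronger things that the protocol does not support:

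- *That later events already sit in the extracts and are thrown away.* Section 6.2 ties extraction to the protocol and SAP, and nothing says that records after month 12 are drawn. They would be available from the same sources if requested.
- *That objective 3 goes unanswered.* It is answered for year one.
- *That PML and other opportunistic infections are affected in the same way.* The latency statement in section 6.9 covers malignancies only, and the protocol nowhere says that infections arise late.
- *That 62% is the expected loss.* It needs uniform uptake, no attrition and the longest study period. It is also a share of person-time, not of events.
- *That the missing time is time under continued exposure.* Section 4.1 gives a recommended schedule ("The recommended maintenance dose is a single 300 mg IV infusion every 6 months thereafter"), but persistence is what objective 2 is meant to find out. Exposure, switching and add-on use are defined only within the 12-month follow-up.

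The extension also has limits. Under linearly rising uptake at T = 57, mean follow-up grows from 9.7 to 19.0 months, which may still be short relative to malignancy latency. Yearly counts of a rare event will meet the small-number masking rules in section 6.7.1. Section 6.9 also notes that other immunosuppressants may themselves raise malignancy risk.

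**Conclusion.** The point holds as a worthwhile improvement, not as an error or an internal contradiction. For malignancies, the protocol has chosen a window that it says may be too short, without giving a reason, although study periods of 41 to 57 months in longitudinal sources would allow more for many patients.

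The limit leaves out about 21% to 62% of the person-time available to the end of the study period. The low to middle part of that range is more plausible, because uptake is expected to rise late. The range rests on assumed entry patterns and attrition, and on later records being obtainable from the sources.

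One related inconsistency does need reconciling whichever window is used. Section 6.7.2.3 states an intention-to-treat approach that disregards discontinuation, while the Table 5 footnote censors at permanent treatment discontinuation.

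**What to change.** 1. Keep 12 months as the main AESI window, so that research question 3 is answered as written.
2. In sections 6.1 and 6.7.2.3 and in Table 5, add a supplementary malignancy incidence rate. Time at risk runs from index date to first malignancy, death, disenrolment or end of the country's study period. Report it overall and, where masking rules allow, by year since index.
3. State that censoring for this rate follows the intention-to-treat rule of section 6.7.2.3, and reconcile the Table 5 footnote with that rule.
4. Make sure that data requests to each source cover the longer period.
5. Amend the statement in section 6.9 that one year is the maximum, and note there that later person-time comes from early initiators.
6. Opportunistic infections including PML may be added in the same way, as an option and not because the protocol calls them late events.

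Cost: a protocol amendment, which may need regulatory approval or ethics notification under section 6.10.1 if judged major; possibly wider data-access wording where committees or project permissions govern access; and an extra set of tables. No further patients are needed. The later person-time will include more patients who have stopped or switched treatment, and may still be short relative to malignancy latency, so it should be read as supplementary.
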